Control Treatment	Mepilex [®] Ag Wound Dressing (Mölnlycke Health Care) is a standardly employed dressing for second-degree/partial-thickness burns due to its non-adherent and antimicrobial properties. The layered dressing includes a flexible, absorbent polyurethane foam pad embedded with silver sulfate compound and vapor permeable film backing with a silicone layer covered with a polyethylene release film.
Phase of Study	Pivotal Study
Proposed Indication for Use	The RECELL Device is indicated for treatment of partial-thickness burns in patients 1 year of age or greater.
Primary Objectives	To demonstrate that RECELL treatment of partial-thickness burn injuries, can safely and effectively increase the incidence of Day 10 healing compared with a standardized wound dressing. Also, the effects of both treatments on the incidence of conventional autografting, pain, itching, scarring, health-related quality of life and resource utilization will be investigated.
Planned Enrollment	To evaluate the primary endpoint, enrollment of 160 subjects is planned.
	This study utilizes an adaptive design with interim analysis for early stopping due to futility or positive outcome and, if necessary, sample size re-estimation in order to maintain adequate condition power. The maximum enrollment will be 300 subjects .
Trial Design	This is a prospective, parallel-arm, randomized (1:1), blinded evaluator, multicenter trial. Infants, children, and adolescents (aged from 1 through 16 years), male and female, with a burn injury that is no more than 30% of their total body surface area (TBSA) and no more than 10% TBSA is full-thickness burn injury, will be considered for participation.
	Randomization and assigned treatment must be performed within 72 hours of the burn injury for a subject to be treated within this study.
	Qualifying subjects will be randomized 1:1 either to treatment with RECELL or to Control (Mepilex [®] Ag Wound Dressing). Randomization will be stratified by investigational site and total burn area (<10% TBSA and \geq 10% TBSA). If there is more than one partial-thickness burn wound, the largest partial-thickness burn wound meeting eligibility requirements will be identified as the Index Burn (the burn wound that will be compared for effectiveness outcomes). The Index Burn will be a contiguous area at least 160 cm ² that excludes the face, hands, feet and genitalia.

In order to evaluate the impact of study treatment on quality of life and health economic outcomes, unless clinical circumstances dictate otherwise, all of the subject's partial-thickness burn wounds, including any non-index burn(s), should be treated at the initial procedure according to the randomized treatment assignment.
For subjects randomized to RECELL, skin sample harvesting and treatment should be performed in accordance with the RECELL Instructions for Use. Prior to application of RES, necrotic tissue is to be excised. The skin sample size required for processing is approximately 1/80 th of the area to be treated. RES may be applied to the RECELL donor site at the investigator's discretion.
For subjects randomized to Control, burn wounds should be cleaned per local standard practice prior to application of Mepilex [®] Ag Wound Dressing. Mepilex [®] Ag Wound Dressing will be applied in accordance with the manufacturer's Instructions for Use.
Subjects should be seen for dressing changes as clinically indicated.
Primary Effectiveness Assessments : Day 10 and Day 28 post-treatment, the Index Burn will be evaluated via direct visualization by a qualified local clinical investigator blinded to treatment allocation (Blinded Evaluator) to assess Index Burn healing, unless the Index Burn has been autografted.
At all follow-up visits, the Index Burn will be photographically documented using standardized digital imaging. From these images, the percent re-epithelialization will be determined via photographic planimetry by a third-party centralized image vendor. A random selection of digital tracings will be reviewed by an Independent Medical Monitor to confirm the correct tracing of re-epithelialized areas reported by a third-party centralized image vendor.
During the acute follow-up period, the investigator will determine whether autografting of the Index Burn is required. Autografting is typically indicated when there are no signs of improvement or healing, when the investigator expects no further wound healing in the next 7 to 11 days, or when a contiguous area greater than 0.5% TBSA is unhealed. Index Burns requiring conventional autografting will be evaluated as clinically indicated.
Standardized digital images of Index Burns taken during acute follow-up, including images taken the day the investigator made a decision to autograft will be presented, out of time sequence, to an Independent Medical Monitor (blinded to treatment allocation and investigator's determination) to review.
Longer-term follow-up visits will be performed at Weeks 8, 16, 24, 36 and 52 post- treatment (irrespective whether a subject had conventional autografting of the Index Burn).
At the Week 16, 24, 36 and 52 post-treatment visits, scar outcomes and disease- specific quality of life will be assessed. Scar outcomes will be measured using the Patient and Observer Scar Assessment Scale (POSAS) questionnaire, which includes components for both the Blinded Evaluator and the subject (or parent/guardian, as appropriate). Patient- and family-reported quality of life outcomes will be captured via the age-specific Burn Outcomes Questionnaire (BOQ). The BOQ evaluates several domains specific to longer-term burn outcomes including physical function, appearance, satisfaction and emotional health among others. Investigator treatment preference will be documented for each treating investigator, at each burn center, following the investigator's last subject's last visit.

	During the longer-term follow-up visits, the preferred method is in-person clinical visits, however (if necessary), these follow-up visits may be conducted remotely (e.g., via telemedicine) with the exception of the Week 52 visit. Treatment-related adverse events (e.g., infection, wound breakdown, etc.) are to be recorded for the Index and Non-Index Burn wounds as well as for donor sites. An interim analysis will be conducted after approximately 50% of total enrollment has reached the primary effectiveness endpoint (i.e., 80 subjects have completed the primary endpoint evaluation including confirmation of healing at Day 28). At that time, study enrollment may be discontinued due to futility or demonstration of effectiveness. If enrollment continues, a sample size re-estimation will be performed, and the sample size may be adjusted upwards to at most 300 subjects.
	A Data Monitoring Committee will be responsible for interim review of safety and effectiveness data and will be responsible for reviewing data from the interim and sample size re-estimation analyses.
Number of Trial Centers	Up to 25 US trial centers with a specialty in pediatric burn care will participate. No center will contribute more than 25% of the total randomized subjects without written Sponsor permission.
Duration of Participation	Each subject will participate in the trial for 52 weeks post-treatment.
Primary Effectiveness Endpoint	The primary effectiveness endpoint is incidence of Index Burns with Day 10 healing post-treatment, evaluated by an observer blinded to treatment allocation, with confirmation at Day 28. If the Index Burn undergoes a secondary surgical treatment for closure (including conventional autografting) prior to the Day 28 visit, this will be considered an endpoint failure.
	The hypothesis to be evaluated is whether the incidence of Day 10 healing post- treatment is greater (superior) with RECELL treatment vs. Control treatment.
Safety Endpoints	Safety will be evaluated in terms of treatment-related adverse events and serious device-related adverse events.
Secondary Effectiveness Endpoints	 Specific secondary endpoints to be investigated for potential labeling claims include the following: 1. Incidence of Index Burn Day 21 post-treatment healing (confirmed on Day 28). 2. Percent area of Index Burn requiring autografting. 3. Incidence of conventional autografting to achieve Index Burn healing. Each endpoint will be tested in a fixed hierarchical method at a one-sided 0.025 significance level in the above order. These secondary endpoints/hypotheses will only be evaluated if the null hypothesis for the primary endpoint is rejected in the appropriate direction, and each secondary endpoint will only be evaluated if the null hypothesis of equality, for the endpoint preceding it in the list above, is rejected in the appropriate direction.
Tertiary Endpoints/ Data Collection	 the appropriate direction. Absolute area (cm²) of Index Burn requiring autografting. Index Burn pain scores at dressing changes assessed by the health care provider performing the dressing change using the Face, Legs, Activity, Cry, Consolability (FLACC) Scale. Subject reported Index Burn pain scores at dressing changes. Percent epithelialization of the Index Burn per digital planimetry. Index Burn POSAS scar ratings. BOQ Outcomes (raw scores and recovery curves for all domains), with baseline at Day 10.

	 Investigator treatment preference. Health economics/medical resource utilization (determined using CRF data in conjunction with UB-04/CMS-1500 and/or similar hospital and physician claim forms for billing purposes to collect data associated with the initial hospital care and readmissions during follow-up as applicable). Index Burn Itch Man Scale ratings.
Pre-Randomization Inclusion Criteria	 Male or female patients aged 1 through 16 years (inclusive) with a partial-thickness thermal burn injury. The patient has a thermal burn injury that is: a. ≤ 30% TBSA (exclusive of superficial areas) and b. ≤ 10% TBSA is a full-thickness burn. The Index Burn must be a clean partial-thickness burn injury ≥160 cm² and between 2-20% BSA (inclusive). The Index Burn may not cover the face, hand, foot or the perineum/genitalia (Note: a patient with wounds in these areas may be enrolled but the Index Burn Area may not include these areas). The patient and/or parent/guardian agrees to comply with all compulsory study procedures and visit schedule. The patient and/or parent/guardian agrees to abstain from any other treatment for closure of the Index Burn for the duration of the study unless medically necessary. The patient and/or parent/guardian agrees to abstain from enrollment in any other interventional clinical trial for the duration of the study. In the opinion of the investigator, the patient and/or parent/guardian must be able to: understand the full nature and purpose of the study, including possible risks and adverse events, Understand instruction, and Provide voluntary informed written consent/assent as appropriate for
Pre-Randomization Exclusion Criteria	 study participation. 1. Not able to understand English or Spanish. 2. Burns caused by chemicals, electricity or radiation. 3. Patients presenting with only 3rd-degree/full-thickness wounds which require immediate autografting. 4. Burn injury has had prior treatment for definitive closure. 5. Patients for whom use of sedation/general anesthesia is not medically appropriate. 6. Superficial/trivial burns or burns that in the investigator's opinion appear to be healing sufficiently such that care under this protocol would be inappropriate. 7. Patient requires immediate or staged surgical procedures for closure of their partial-thickness burns. 8. Conditions, e.g., previous burn injury to study area, poor nutritional status, poorly controlled diabetes mellitus (HbA1c >9%), that in the investigator's opinion may compromise subject safety or trial objectives. 9. Current use of medications, e.g., immunosuppressive agents (excluding inhaled corticosteroids), that in the investigator's opinion may compromise subject safety or trial objectives. 10. Inhalation injury. 11. Active infection, cellulitis or need for immediate grafting at the planned treatment areas. 12. Concerns for parent/guardian's ability to provide appropriate follow-up care. 13. Subjects with a known hypersensitivity to trypsin or compound sodium lactate for irrigation solution. 14. Subjects with a known sensitivity to silver.

Post-Randomization (Prior to treatment) Eligibility Criteria	 In post-pubescent girls, pregnant or breast-feeding (pregnancy test should be performed in accordance with local institutional requirements). Immediate life-threatening condition or life expectancy less than one year. Previous randomization within this investigation. Post-Randomization Inclusion: Patient randomized (and will be treated) within 72 hours from the time of the burn injury. Patient continues to meet all pre-randomization inclusion criteria.
	 Post-Randomization Exclusion: 1. Incidental finding of any pre-randomization exclusion criteria. Consented subjects who do not meet the post-randomization eligibility criteria and did not receive study treatment will be followed through the Day 28 visit and then withdrawn from the study. The criteria for which exclusion was based will be
Statistical Considerations	documented. Based on medical input, the estimated proportion of subjects with confirmed day 10 healing is anticipated to be approximately 75% for the Control group. It is estimated that the proportion of RECELL subjects with confirmed day 10 healing will be 92.5%. Assuming power of 80%, using a one-sided z-test of proportions and one-sided alpha of 0.025 requires 69 subjects per group (138 subjects total). The total sample size has been increased by 12% to 160 subjects to adjust for missing data.
	The hypothesis to be evaluated is whether the incidence of Day 10 healing post- treatment (confirmed at Day 28 post-treatment) is greater (superior) with RECELL treatment vs. Control treatment.
	A formal unblinded interim analysis comparing treatments on the primary endpoint will be conducted once 50% of total enrollment has completed the primary effectiveness endpoint follow-up (i.e., 80 subjects have been randomized and reached the Day 28 healing confirmatory visit or would have reached the Day 28 visit had they not prematurely withdrawn).
	The unblinded interim analysis will be based on O'Brien-Fleming stopping rules. At the interim look, the one-sided p-value will need to be less than or equal to 0.00153 with results favoring RECELL in order to stop the study for reasons of overwhelming effectiveness of RECELL; the one-sided p-value will need to exceed 0.45604 to stop the study for futility. The one-sided p-value at the final analysis needs to be less than or equal to 0.02496, rather than the usual 0.025 required for a study without an interim analysis. This interim analysis will be based on patients with available primary endpoint data; there will no imputation of missing data at this interim analysis.
	The Intent to Treat (ITT) population will consist of all enrolled subjects who are randomized, with data analyzed according to randomized treatment assignment.
	The Modified Intent to Treat (mITT) Population will consist of all enrolled subjects who are randomized and treated, with data analyzed according to randomized treatment assignment. This population will be utilized as a primary analysis population for the primary and secondary effectiveness endpoints.
	Per Protocol (PP) Population will consist of mITT subjects who do not have major protocol deviations with data analyzed according to treatment received. This population will be utilized as a secondary analysis population for the primary and secondary effectiveness endpoints.

The primary effectiveness endpoint is incidence of Index Burns with Day 10 healing, evaluated by an observer blinded to treatment allocation, with confirmation at Day 28. If the Index Burn undergoes a secondary surgical treatment for closure (including conventional autografting) prior to the Day 28 visit, this will be considered an and noist foilure.
endpoint failure.

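### The final cut-off of 0.02496 holds one-sided 0.025 only if futility is binding and the final test allows for a sample size chosen from unblinded data; the synopsis states neither

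*Combined protocol and SAP*

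**What the plan says.** All references are to the protocol synopsis, the only part of the plan available for this review.

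- **Interim (Statistical Considerations).** "A formal unblinded interim analysis comparing treatments on the primary endpoint will be conducted" once 80 subjects have reached, or would have reached, Day 28. The trial can stop for effectiveness at one-sided p of 0.00153 or less. For futility, "the one-sided p-value will need to exceed 0.45604 to stop the study for futility".
- **Final analysis (same row).** "The one-sided p-value at the final analysis needs to be less than or equal to 0.02496". The reason given for not using 0.025 is the interim look; re-estimation is not mentioned there.
- **Re-estimation.** Planned Enrollment provides for "if necessary, sample size re-estimation in order to maintain adequate condition power". Trial Design says: "If enrollment continues, a sample size re-estimation will be performed, and the sample size may be adjusted upwards to at most 300 subjects".
- **Stopping (Trial Design).** "At that time, study enrollment may be discontinued due to futility or demonstration of effectiveness".
- **Test.** A test is named only in the sample size calculation: "using a one-sided z-test of proportions and one-sided alpha of 0.025 requires 69 subjects per group".

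The synopsis gives no final test statistic, no conditional power target, no effect size at which conditional power is evaluated, no range of interim results in which N may rise, and no statement that futility is binding.

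**The concern.** The new sample size is chosen by people who have seen the treatment difference. If the final analysis then pools all subjects in an ordinary z-test, the interim data carry a weight that depends on their own value. A weak interim result is diluted by a larger second stage, and the chance of a false positive after that result rises. After a stronger result, a larger N lowers that chance. Whether the total stays at 0.025 depends on where N is raised, and the synopsis does not say.

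Futility is a separate gap. The futility bound pays for part of the final cut-off, so 0.02496 is correct only if crossing the bound always ends the trial.

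At stake is the type I error of a pivotal superiority claim. The three secondary endpoints intended for labeling are tested only if that claim succeeds.

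**Working it through.** **Inputs from the synopsis.** Interim n1 = 80; planned N = 160; maximum 300; one-sided p bounds 0.00153, 0.45604 and 0.02496; design rates 75% and 92.5%; one-sided alpha 0.025; power 80%. **Assumed:** a conditional power target of 80% (the synopsis gives 80% only as design power), with conditional power evaluated at the observed trend.

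**1. The plan's own figures.**
- Sample size, pooled z-test: mean rate 0.8375; n = [1.960·√(2·0.8375·0.1625) + 0.842·√(0.75·0.25 + 0.925·0.075)]² / 0.175² = 68.6, so 69 per group. This agrees.
- Interim bound, O'Brien-Fleming-type spending at half the information: 2·[1 − Φ(2.241/√0.5)] = 0.001525, against 0.00153 stated. This agrees.
- As z-values the bounds are c1 = 2.962 (effectiveness), f = 0.110 (futility) and c2 = 1.961 (final).

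**2. Level at a fixed N of 160.** Given interim value z, the null probability that the pooled z-statistic at size N exceeds c2 is

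A(z, N) = 1 − Φ[(c2·√N − z·√80) / √(N − 80)].

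The level is 0.00153 + ∫ φ(z)·A(z, N) dz, taken from f to c1 if futility is binding and from −∞ to c1 if it is not. With N = 160:
- binding: 0.0250
- non-binding: 0.0255

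So 0.02496 presumes binding futility. With non-binding futility the matching cut-off is about 0.0245.

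**3. Why the rule matters.** Compare A at the two ends of the permitted range:

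| Interim z | A(z, 160) | A(z, 300) |
|---|---|---|
| 0.5 | 0.0115 | 0.0234 |
| 1.0 | 0.0381 | 0.0458 |
| 1.6 | 0.1204 | 0.0926 |

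Raising N to 300 increases the false-positive chance when z is below about 1.22 and lowers it above.

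**4. Level with re-estimation.** Use the same integral with N(z) between 160 and 300. Conditional power at the observed trend is

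CP(z, N) = 1 − Φ[(c2·√N − z·√80 − (N − 80)·z/√80) / √(N − 80)].

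CP at 300 first reaches 80% at z = 1.385 (one-sided p = 0.083), where CP at 160 is about 0.50.

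| Rule, ordinary z-test at 0.02496 | Binding | Non-binding |
|---|---|---|
| No re-estimation | 0.0250 | 0.0255 |
| N raised to the size needed, capped at 300, after every continuing result short of 80% | 0.0278 | 0.0304 |
| N raised only if 80% is reachable by 300 | 0.0245 | 0.0249 |
| Largest value over all rules, N 160 to 300 | 0.0285 | 0.0311 |

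The 0.0304 needs futility to be overridden and N enlarged there as well. If N stays at 160 in that region it is 0.0282. With a 90% target the second and third rows are 0.0270 / 0.0296 and 0.0241 / 0.0246.

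**5. Fixed-weight statistic.** With √0.5·Z1 + √0.5·Z2, A no longer depends on N. The level is 0.0250 (binding, 0.02496), 0.0255 (non-binding, 0.02496) or 0.0250 (non-binding, 0.0245), whatever the re-estimation rule.

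**6. Binomial check.** Simulation at common healing rates of 0.70, 0.75 and 0.80, 80% target, binding futility:
- no re-estimation: 0.0250 to 0.0258
- N raised after every continuing result short of 80%: 0.0277 to 0.0281
- N raised only if 80% is reachable: 0.0245 to 0.0252
- fixed-weight test: 0.0252 to 0.0257

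At a common rate of 0.925 the first three fall to 0.0221, 0.0256 and 0.0219.

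**The case against.** - **Only the synopsis was available.** A combined protocol and SAP would normally put the final statistic and the conditional power rule in the body. This stands. A reader might infer that the plan lacks these items altogether, and the available text does not support that.
- **The inflating rule is the least natural reading.** Planned Enrollment qualifies re-estimation as needed only where necessary, and Trial Design says N may rise, not that it must. This stands in part: no passage states a rule without a floor. But no passage excludes one either, since the only lower limit given is the futility bound.
- **Futility is probably meant to be binding.** The permissive wording in Trial Design covers stopping for effectiveness too, so it may simply list outcomes, and 0.02496 itself points to binding. That is a fair reading, but it has to be inferred.
- **The effect is small.** Under binding futility the excess is at most 0.0285 − 0.0250 = 0.0035 under any rule. Discreteness alone moves the plain design by up to about 0.0008 above 0.025 at rates of 0.70 to 0.80. This stands and limits the severity.

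Two stronger inferences also fail. The cut-off 0.02496 is not wrong: it is right for the fixed design with binding futility. And 0.0245 to 0.0278 is not the range of possible levels: it comes from two illustrative rules under an assumed target.

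**Conclusion.** The point holds as a should-fix. Taken literally, the synopsis allows versions of the design that hold one-sided 0.025 and versions that do not, and 0.02496 is justified only by the interim look. For the two illustrative rules with binding futility, the level differs from 0.025 by −0.0005 to +0.0028. Overriding futility and enlarging N there takes the inflating rule to 0.0304. These figures rest on an ordinary z-test being the final test (inferred from the sample size calculation), an 80% target at the observed trend, and the normal approximation. Confidence is medium because the SAP body was not available.

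**What to change.** Settle the following before anyone sees unblinded interim data.

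1. **Final statistic.** Pre-specify the fixed-weight inverse-normal (Cui-Hung-Wang) statistic √0.5·Z1 + √0.5·Z2. Z1 uses the subjects in the interim analysis. Z2 uses all others, including those enrolled but not yet at Day 28 at the interim. The weights stay fixed whatever the final N.
2. **Futility.** Declare it binding and keep 0.02496, or non-binding and use about 0.0245. The level is then 0.025 asymptotically for any re-estimation rule; discreteness may add up to about 0.0008, as it does for the plain design.
3. **Alternative.** Keep the ordinary z-test and pre-specify a restricted rule, such as raising N only if a size up to 300 reaches the target. Confirm its level by exact or simulated binomial calculation.

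**Cost.** Some SAP wording and a few lines of code. Power below is by normal approximation with an 80% target and binding futility. If N is raised after every continuing result short of the target, the weighted test has 94.5% against 94.7% for the ordinary test at 75% vs 92.5% healing, 85.3% against 86.2% at 75% vs 90%, and 69.3% against 71.1% at 75% vs 87.5%. Using 0.0245 costs a further 0.1 to 0.3 points. The restricted rule costs more because fewer weak interim results are enlarged: at 75% vs 92.5% the ordinary test has 88.1% (mean N 149) against 94.7% (mean N 176).

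If the SAP body already fixes these items, only a cross-reference is needed.

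### The stated safety endpoints count only events judged related, with no all-cause comparison by arm and no statement of who judges relatedness or whether that person is blinded

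*Combined protocol and SAP*

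**What the plan says.** The Safety Endpoints entry of the protocol synopsis reads: "Safety will be evaluated in terms of treatment-related adverse events and serious device-related adverse events". Both parts depend on a causality judgement. The Trial Design entry, just after the description of the longer-term visits, says: "Treatment-related adverse events (e.g., infection, wound breakdown, etc.) are to be recorded for the Index and Non-Index Burn wounds", and extends this to donor sites.

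On blinding, Trial Design states: "This is a prospective, parallel-arm, randomized (1:1), blinded evaluator, multicenter trial". The Blinded Evaluator's tasks are Index Burn healing ("evaluated via direct visualization by a qualified local clinical investigator blinded to treatment allocation (Blinded Evaluator) to assess Index Burn healing") and the observer part of the scar scale. A second blinded role is the "Independent Medical Monitor (blinded to treatment allocation and investigator's determination) to review" images of the Index Burn, including those from the day of a decision to autograft. Neither role is given adverse event causality.

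The arms differ visibly: "For subjects randomized to RECELL, skin sample harvesting and treatment should be performed in accordance with the RECELL Instructions for Use", with necrotic tissue excised first, whereas Control wounds are cleaned and dressed. On oversight: "A Data Monitoring Committee will be responsible for interim review of safety and effectiveness data".

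**The concern.** The Primary Objectives entry makes safety part of the claim and sets it against a standard dressing, so the safety question is comparative. Randomization protects a comparison of all events between arms. It does not protect a comparison of the subset that someone, after treatment, has judged to be caused by that treatment. If the share of events judged related differs by arm, the related-event rates differ even when the true rates do not.

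Two features make this more than theoretical. Infection and wound breakdown, the examples in the recording sentence, can arise from the burn itself, so relatedness is a matter of judgement. And a wound that has been excised and sprayed may prompt a different judgement from one that has been dressed. If the recording sentence is applied literally, an event judged unrelated might never be entered, and a later all-event table could not recover it.

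The serious-event endpoint has a further gap. The available text does not say whether device-related covers the Control dressing, so that endpoint may have no like-for-like comparator.

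**Working it through.** The documents give no adverse event rate, attribution rate, safety hypothesis or margin, so there is no safety figure to reproduce. The check has two parts.

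**1. The text, side by side**

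- Endpoint definition (Safety Endpoints): related events and serious device-related events. All-cause events are not named.
- Recording (Trial Design): treatment-related events at index wounds, non-index wounds and donor sites. Unrelated events are not mentioned.
- Blinded roles (Trial Design): healing, scar rating and image review. Causality is assigned to neither.
- Data Monitoring Committee: reviews interim safety data. Causality adjudication is not mentioned.
- Who judges relatedness: not stated.

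The restriction in the endpoints is therefore textual. That the person judging relatedness knows the arm is an inference from the evaluator-only design and the visible skin harvest.

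**2. Size, on assumed rates**

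Observed related rate = true rate × proportion attributed. It follows that the observed rate ratio = true rate ratio × attribution ratio.

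*A difference created (equal true rates of 20%):*

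- 50% and 50% attributed: 0.20 × 0.50 = 10% in both arms.
- 80% and 50%: 0.20 × 0.80 = 16%; 0.20 × 0.50 = 10%.
- 60% and 30%: 0.20 × 0.60 = 12%; 0.20 × 0.30 = 6%.
- 80% and 40%: 0.20 × 0.80 = 16%; 0.20 × 0.40 = 8%.

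Swapping the arms reverses the sign.

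*A difference hidden (true rates 25% RECELL, 15% Control):*

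- 50% and 80% attributed: 0.25 × 0.50 = 12.5%; 0.15 × 0.80 = 12.0%. A 10-point excess appears as 0.5 points. Ratio check: (25/15) × (50/80) = 1.667 × 0.625 = 1.04 = 12.5/12.0.

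*Chance of an apparent signal.* Take 80 per arm (160 planned, 1:1) and a nominal two-sided 0.05 comparison, which the plan does not specify. The chance of significance in the over-attributed direction is

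Φ{ [d − 1.96 √(2p̄(1−p̄)/80)] / √([p₁(1−p₁) + p₂(1−p₂)]/80) }, where d = p₁ − p₂ and p̄ is the mean of the two rates.

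- Equal attribution: 2.5%.
- 16% vs 10%: (0.06 − 1.96 × 0.0532)/0.0530 = −0.83, so about 20%.
- 12% vs 6%: (0.06 − 1.96 × 0.0452)/0.0450 = −0.64, so about 26%.
- 16% vs 8%: (0.08 − 1.96 × 0.0514)/0.0510 = −0.41, so about 34%.

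On these assumptions, a purely attributional signal arises 8 to 14 times as often as the nominal 2.5% (20/2.5 = 8; 34/2.5 = 13.6).

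**The case against.** The strongest objection is that the available text is a synopsis. It contains no adverse event definitions, reporting section or safety analysis section, and a one-line endpoint entry does not show that other events go uncollected. The recording sentence does not say that only related events are entered, and its position leaves open whether it governs the acute period. This stands as a limit on the claim: one might infer that unrelated events will be lost, and the documents do not establish that. It does not change how the endpoints are defined.

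Other stronger readings also go too far:

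- *That investigators who know the arm judge relatedness.* This is likely, but no section says who does it.
- *That only the healing evaluator is blinded.* The Independent Medical Monitor is blinded too, though for images.
- *That donor-site events can occur only under RECELL.* Conventional autografting is an outcome in both arms, so Control subjects can have donor sites. Only the RECELL skin-harvest sites are specific to one arm.
- *That the bias favours RECELL.* The illustrations run both ways, and nothing in the documents sets the direction.

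There are partial safeguards. The Data Monitoring Committee reviews safety data, and autografting, pain, itch and readmissions are collected without a relatedness filter. These help, but they are not all-cause event tables, and the committee can review only what has been recorded. It is also true that no formal safety test is stated, so no decision rule is corrupted, and that all-event counts remain open to unblinded detection and reporting. The proposed change removes the attribution step, not every source of bias.

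**Conclusion.** The point holds as a limitation of the stated endpoints that is cheap to correct. The comparative safety claim rests on events filtered through a post-treatment causality judgement, by an assessor whose identity and blinding are not stated, with no all-cause comparison named.

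The size cannot be derived from the documents. With assumed true rates of 15% to 25% and attribution of 50% to 80%, a 10-point excess can shrink to 0.5 points, or a 6-point difference can appear where none exists. If attribution is equal in the two arms, spurious differences disappear and true ones are only scaled down. The documents do not show that attribution will differ, that harm would be concealed, or that event collection is in fact incomplete.

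**What to change.** - **Endpoints and analysis:** report all adverse events and all serious adverse events by arm regardless of attribution, and state the analysis population. Keep treatment-related and serious device-related events as subset tables.
- **Recording:** reword the Trial Design sentence so that wound-site events, donor-site events and all serious events are entered whether or not they are judged related, and make clear which follow-up period it covers.
- **Donor sites:** tabulate these events separately, distinguishing RECELL harvest sites from autograft donor sites, so that burn-site events are compared like with like.
- **Attribution:** state who judges relatedness and whether that person is blinded, and define device-related for both arms.

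The cost is protocol and SAP wording, some extra event entry, and longer listings dominated by background burn-care events. If fuller collection is already specified elsewhere in the protocol, only the endpoint and analysis wording needs to change.
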